32.0 Humanitarian Use Devices

N/A: This study does not involve humanitarian use devices. This does not apply.

32.1 For Humanitarian Use Device (HUD) uses provide a description of the device, a summary of how you propose to use the device, including a description of any screening procedures, the HUD procedure, and any patient follow-up visits, tests or procedures.

Response:

32.2 For HUD uses provide a description of how the patient will be informed of the potential risks and benefits of the HUD and any procedures associated with its use.

Response:

University at Buffalo Institutional Review Board (UBIRB)

Office of Research Compliance | Clinical and Translational Research Center Room 5018
[name]

Title: Impact of Brain Connectome and Personality on Cognitive Rehabilitation
in Multiple Sclerosis

Statistical analyses will be performed using SPSS 22.0 (IBM Inc., Armonk, NY, USA) and R 3.4.1 (The R Foundation).

[1a] Determine whether low Conscientiousness predicts lesser overall cognitive improvement following cognitive rehabilitation in people with MS. The question of whether Conscientiousness predicts successful intervention will be addressed using baseline measures of trait Conscientiousness and cognitive performance before and after rehabilitation. We will assess linear relationships between baseline trait Conscientiousness and overall magnitude of cognitive improvement using linear regression models. Cognitive improvement will be measured according to differences in cognitive scores between baseline assessment during visit 1 and post-rehabilitation assessment at visit 2. In order to summarize results across all cognitive measures, test scores will be converted to normalized z-scores and averaged together.

[1b] Determine whether the impact of Conscientiousness on cognitive rehabilitation is moderated by executive function and treatment adherence. In order to address the question of whether or not adherence and executive function moderate the impact of Conscientiousness on intervention success, we intend to add interaction parameters to the linear regression analysis described for aim 1a. For instance, we will calculate the interaction variable between Conscientiousness and DKEFS-ST (executive function) and include it in our regression models.

[2] Identify structural and functional brain connectome characteristics which predict successful improvement in sub-domains of cognition following rehabilitation. In order to identify brain connectome characteristics which predict specific responses to sub-domains of cognition following rehabilitation, we intend to employ linear machine/statistical learning techniques, such as partial least squares regression. The correct statistical learning models will be identified at the time of analysis in order to produce the most appropriate predictions. Models will be selected according to the distribution and dimensionality of our connectome variables. Following training of the predictive models, fit of the models will be assessed using k-fold cross validation.

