3.0 Background

3.1 Provide the scientific or scholarly background, rationale, and significance of the research based on the existing literature and how it will contribute to existing knowledge. Describe any gaps in current knowledge. Include relevant preliminary findings or prior research by the investigator.

Response: The personality trait Conscientiousness is a behavioral phenotype encompassing the proclivity for achievement striving, organization, and deliberation in daily activity. Trait Conscientiousness is operationally measured using the NEO Five Factor inventory (NEO-FFI), a model of personality widely studied in MS and other neurological populations.¹ Trait Conscientiousness is normally distributed in humans, shows substantial cross-observer agreement, and has a similar mean and range across different cultures.^{2,3}

Decreased Conscientiousness relative to healthy controls (HCs) has been observed in people with multiple sclerosis (pwMS)⁴, an autoimmune disease that involves both neuroinflammation and neurodegeneration.⁵ It is important to study Conscientiousness decline in pwMS because preliminary findings suggest that **Conscientiousness predicts poor adaptation and unfavorable disease outcomes in neurological disease**. For instance, Conscientiousness predicts CD4 count and viral load over 1-year in HIV disease.⁶ Lower Conscientiousness is associated with increased risk of amnestic mild cognitive impairment, and transition to Alzheimer's dementia over 12 years.⁷ This trait also correlates negatively with mortality risk among older adults following stroke.⁸ Low baseline Conscientiousness is also associated with increased risk of poor disease outcomes in non-neurological diseases. For instance, adults with prediabetes and low Conscientiousness are more likely to later develop type II diabetes, and children with type I diabetes and low Conscientiousness exhibit worse glycemic control.^{9,10} Notably, **low Conscientiousness is also associated with reduced success of behavioral interventions on health behaviors and disease outcomes**. For example, low Conscientiousness is prospectively associated with reduced improvement in medication adherence, emotional burden, and physical activity, following a range of behavioral interventions in adults with diabetes.¹¹

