In order to address our second goal, we will use a multi-parametric approach in which we account for cerebral pathology, such as regional gray matter atrophy, microstructural white matter damage, lesion volume and localization, white matter tract integrity and structural connectivity, and resting state functional connectivity. We will apply network-based analysis, where appropriate, in order to account for network-level organization of the brain. These methods of analysis are well-suited for elucidating patterns of insult which lead to changes in complex emergent phenomenon such as higher level cognition.

Our results may provide foundation for better directing rehabilitation and behavioral treatments. For instance, a short questionnaire could be used to identify patients whose personality profile puts them at greater risk for unfavorable disease progression. An understanding of this risk could help direct efforts which mitigate against these unfavorable outcomes. Similarly, baseline patterns of cerebral pathology could also be employed to predict responses to the cognitive and other behavioral interventions. There is a burgeoning interest in personality trait adaptation and personalized health plans among health care agencies²² and we believe our research will contribute meaningfully to this growing field of interest.

3.2 Include complete citations or references.

Response:

2. McCrae RR. Trait psychology and culture: exploring intercultural comparisons. *J Pers*. 2001;69(6):819-846.
doi:10.1037/0022-3514.52.1.81.

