6.0 Inclusion and Exclusion Criteria

*6.1 Describe the criteria that define who will be **included** in your final study sample.*

NOTE: This may be done in bullet point fashion.

Response:

For all subjects:

- males and females above age 18
- fluent in English
- education >9 years

Additional inclusion criteria for MS patients are as follows:

- Clinically definite MS diagnosis
- Expanded Disability Status Scale (EDSS) ≤ 6.5
- MS patients must be relapse-free and stable from the time of their MRI acquired for the CEG-MS study
- Willing and able to comply with the study procedures for the duration of the trial

*6.2 Describe the criteria that define who will be **excluded** from your final study sample.*

NOTE: This may be done in bullet point fashion.

Response:

- history of serious medical or psychiatric illness (other than MS in the patient group) that may affect cognitive functioning
- color-blindness

- history of developmental disability
- past or current alcohol or substance dependence
- History of major depressive disorder, bipolar disorder, or psychotic disorder predating the onset of MS
- History of traumatic brain injury as defined by trauma causing loss of consciousness or transient post-traumatic or retrograde amnesia exceeding 5 min
- Other pathology related to MRI abnormalities

6.3 *Indicate specifically whether you will include any of the following special populations in your study using the checkboxes below.*

NOTE: Members of special populations may not be targeted for enrollment in your study unless you indicate this in your inclusion criteria.

Response:

- Adults unable to consent
- Individuals who are not yet adults (infants, children, teenagers)
- Pregnant women
- Prisoners

6.4 *Indicate whether you will include non-English speaking individuals in your study. Provide justification if you will exclude non-English speaking individuals.*

*In order to meet one of the primary ethical principles of equitable selection of subjects, non-English speaking individuals may **not** be routinely excluded from research as a matter of convenience.*

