If an individual is ineligible for participation, their screening information will be discarded (i.e., shredded). If participants are deemed eligible (either in person or over the phone), they will be scheduled to come in to the hospital for neuropsychological testing. Written consent will be obtained prior to administration of tests. As part of the consent process, participants will be asked for permission to use any data collected as part of the screening process as well.

10.2 Describe what data will be collected.

NOTE: For studies with multiple data collection points or long-term follow up, consider the addition of a schedule or table in your response.

Response: Demographic/social history, health history (as provided by participants during screening, review of medical records, etc.), and cognitive test data.

10.3 List any instruments or measurement tools used to collect data (e.g. questionnaire, interview guide, validated instrument, data collection form).

Include copies of these documents with your submission.

Response: Below is a list of neuropsychological tests that will be included. Symbol Digit Modalities Test (SDMT), California Verbal Learning Test 2nd Edition (CVLT), Brief Visuospatial Learning Test Revised (BVMT-R), Delis-Kaplan Executive Function System [DKEFS] Sorting Test, Delis-Kaplan

Executive Function System [DKEFS] Tower Test. Self-report/informant-report surveys have been uploaded. Self-report measures include the Beck Depression Inventory-Fast Screen (BDI-FS), Multiple Sclerosis Neuropsychological Questionnaire (MSNQ), Fatigue Severity Scale (FSS), NEO-FFI personality inventory, Multiple Sclerosis Quality of Life (MSQoL) and Elithorn's Perceptual Maze Test (EPMT). Informant-report measures include the NEO-FFI.

10.4 Describe any source records that will be used to collect data about subjects (e.g. school records, electronic medical records).

Response: We will be collecting MRI and EDSS information for subjects from the database of IRB no. 603069 of CEG- MS study.

*10.5 Indicate whether or not **individual** subject results, such as results of investigational diagnostic tests, genetic tests, or incidental findings will be shared with subjects or others (e.g., the subject's primary care physician) and if so, describe how these will be shared.*

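### Aim 1a can show whether Conscientiousness predicts training gain, but no prespecified model shows whether it adds to the disease burden (EDSS, MRI) already on file

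*SAP*

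**What the plan says.** SAP [1a], repeated in Protocol 17.1, gives the analysis as: "We will assess linear relationships between baseline trait Conscientiousness and overall magnitude of cognitive improvement using linear regression models". The outcome is the visit 1 to visit 2 difference, averaged over z-scored tests. No covariate is listed.

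Aim 1b adds interaction terms for executive function and adherence. Its example is that "we will calculate the interaction variable between Conscientiousness and DKEFS-ST (executive function) and include it in our regression models". No EDSS or MRI term is mentioned.

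Aim 2 has its own models for the connectome predictors: "we intend to employ linear machine/statistical learning techniques, such as partial least squares regression". Conscientiousness is not named as a predictor there. Protocol 3.1 places brain damage under that aim: "In order to address our second goal, we will use a multi-parametric approach in which we account for cerebral pathology".

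The burden data will be in hand. Protocol 10.4 says "We will be collecting MRI and EDSS information for subjects from the database" of the parent CEG-MS study, and 9.1 directs recruitment to people who completed the MRI there. Disability may range widely, since 6.1 admits "Expanded Disability Status Scale (EDSS) ≤ 6.5".

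**The concern.** Three statements in the protocol, read together, make disease burden a plausible confounder of the aim 1a slope. Section 3.1 reports lower Conscientiousness in MS than in healthy controls and adds "It is important to study Conscientiousness decline in pwMS". The same section reports that lower Conscientiousness goes with slower processing, which it treats as the leading cognitive deficit of MS. Hypothesis 2a in 1.2 expects connectome disturbance to explain part of the response to rehabilitation. If more severe disease goes with both lower Conscientiousness and smaller gain, an unadjusted slope will carry some of that.

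What is at stake is interpretation. Section 3.1 wants to demonstrate the value of personality assessment for risk stratification and for directing interventions, and it envisages a short questionnaire. A natural question for a reader of the results is whether the questionnaire tells the clinician more than the EDSS and MRI already do. The plan names no analysis that answers it. Section 3.1 itself cites an earlier Conscientiousness result, on employment, that held after control for cognitive impairment and depression. Aim 1a specifies no comparable control.

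**Working it through.** **1. The plan's own figure.** Protocol 17.2 gives an effect size of 0.38, 80% power and 41 participants. The metric, alpha and sidedness are not stated. Reading 0.38 as a correlation and assuming alpha 0.05, the Fisher z formula is N = ((z_alpha + z_power) / atanh(r))² + 3, with atanh(0.38) = 0.400.
- One-sided: ((1.645 + 0.842) / 0.400)² + 3 = 41.6. Simulated power at 41 is 0.80.
- Two-sided: ((1.960 + 0.842) / 0.400)² + 3 = 52.0, rounded up to 53.

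So 41 is reproduced, to within one participant, as a one-predictor correlation at one-sided 5%. On this reading the sizing has no burden term in it.

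**2. What burden alone could produce.** The documents give no correlation between burden and either variable, so these are assumptions. Let burden correlate −a with Conscientiousness and −b with gain, with no direct effect of Conscientiousness. The marginal correlation is then r = a × b. With n = 50 (the enrolment target in 5.1, all completing), the chance of a significant slope is approximately P(Z > z_alpha − atanh(r) × √47). The two-sided figures also count the small lower tail.

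| a = b (assumed) | r = a × b | atanh(r) × √47 | one-sided 5% | two-sided 5% |
|---|---|---|---|---|
| 0.2 | 0.04 | 0.27 | 9% | 6% |
| 0.3 | 0.09 | 0.62 | 15% | 9% |
| 0.4 | 0.16 | 1.11 | 30% | 20% |
| 0.5 | 0.25 | 1.75 | 54% | 42% |

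Simulated trials agree to within about one percentage point.

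**3. What adjustment would achieve.** If burden is measured without error and included, the rate returns to 5%. It will not be measured without error. If the recorded measure has reliability 0.5 (assumed) and a = b, the remaining partial correlation is 0.5a² / (1 − 0.5a²). This is 0.047, 0.087 and 0.143 for a = 0.3, 0.4 and 0.5. With one covariate √47 becomes √46, and the one-sided rates are about 9%, 15% and 25%. Adjustment reduces the problem but does not remove it.

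**4. What adjustment would cost.** With two covariates and n = 50, power is P(Z > z_alpha − atanh(partial r) × √45).
- Partial r = 0.38: 0.85 one-sided and 0.77 two-sided, against 0.86 and 0.78 unadjusted.
- Partial r = 0.30: 0.67 one-sided and 0.55 two-sided.

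The two degrees of freedom cost almost nothing. A real loss comes only if part of the association is shared with burden, and then a wide adjusted interval is likely.

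**The case against.** The strongest reply is that aim 1a asks a predictive question. Section 2.1 calls the primary end-points predictive, and a marker that works because it reflects pathology still predicts. This stands: the unadjusted regression is the right primary analysis for that question. It also follows that the percentages in the table are not false-positive rates of aim 1a, although a reader might infer that. Where r is 0.04 to 0.25, the null of no linear relationship is false, and the percentages are chances of detecting a real marginal association. They become errors only for a claim of an effect independent of burden.

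A reader might also infer that the protocol's premises establish MS pathology as a common cause. They do not. Section 3.1 compares patients with healthy controls and does not say that lesion load, atrophy or EDSS grades Conscientiousness among patients, who are the only people enrolled. Hypothesis 2a concerns connectome disturbance and gives no direction. Section 3.1 also raises a reverse path, in which low Conscientiousness leads to poorer adherence to disease-modifying treatment. If burden lies on that path, adjustment removes part of the effect of interest.

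Finally, it would be too strong to say that the plan keeps personality and pathology out of one model. It refers to regression models in the plural and lists no covariates, so a joint model is unspecified rather than barred.

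What survives is narrower. No analysis of added value is prespecified, although the stated goal and the impact wording of aim 1b invite that reading.

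**Conclusion.** The point holds as a gap in what can be concluded, not as an error in the primary analysis. From the planned model the trial can report whether Conscientiousness predicts gain. It cannot report whether Conscientiousness predicts gain beyond EDSS and MRI.

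The possible size runs from negligible to large: 9% to 54% one-sided, or 6% to 42% two-sided, for burden correlations of 0.2 to 0.5 on both sides, with 50 completers and no direct effect. The correlations, alpha and sidedness are all assumed, and nothing in the documents favours the upper end. The change is worth making because the data are already to be collected and the primary analysis stays as it is.

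**What to change.** - Keep the unadjusted aim 1a regression as primary, and state its alpha and sidedness.
- Prespecify one secondary model: change = Conscientiousness + EDSS + one global MRI burden measure from CEG-MS (for example lesion volume or normalised brain volume). Choose the measure before visit 2 data are linked.
- Report the Conscientiousness slope from both models with confidence intervals.
- Do not claim prediction beyond disease burden from the unadjusted slope alone. Treat an adjusted interval that includes zero as inconclusive, not as evidence that the questionnaire adds nothing.
- State the limits. Confounding may remain because the burden measures are imperfect or predate visit 1, although 6.1 requires patients to be relapse-free and stable since the parent-study MRI. Over-adjustment is possible if low Conscientiousness itself raises burden through poor treatment adherence. An adjusted interval that excludes zero is therefore supportive rather than conclusive.

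The cost is a short addition to the SAP and two degrees of freedom in a secondary model. No new data collection is needed.

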1.0 Objectives

1.1 *Describe the purpose, specific aims, or objectives of this research.*

Response: The specific aims of this study are:

[1a] Determine whether low Conscientiousness predicts lesser overall cognitive improvement following cognitive rehabilitation in people with MS.

[1b] Determine whether the impact of Conscientiousness on cognitive rehabilitation is moderated by executive function and treatment adherence.

[2] Identify structural and functional brain connectome characteristics which predict successful improvement in sub-domains of cognition following rehabilitation.

This study will also serve to supplement the sample of participants for the current IRB approved study ((IRB: 603069, Title: *A case-control, 5-year follow-up study of cardiovascular, environmental and genetic risk factors for disease progression in patients with multiple sclerosis (CEG-MS study)*).

1.2 *State the hypotheses to be tested, if applicable.*

NOTE: A hypothesis is a specific, testable prediction about what you expect to happen in your study that corresponds with your above listed objectives.

Response:

[1a] We expect that individuals with low baseline Conscientiousness will experience a lower magnitude of overall cognitive improvement following rehabilitation

[1b] We expect the impact of Conscientiousness on fidelity of rehabilitation will in part be moderated by individual differences in program adherence and executive function

[2a] We expect that individual differences in structural and functional connectome disturbances will in part explain differences in participant responses to cognitive rehabilitation.

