2.0 Scientific Endpoints

2.1 Describe the scientific endpoint(s), the main result or occurrence under study.

*NOTE: Scientific endpoints are outcomes defined before the study begins to determine whether the objectives of the study have been met and to draw conclusions from the data. Include primary and secondary endpoints. Some example endpoints are: reduction of symptoms, improvement in quality of life, or survival. Your response should **not** be a date.*

Response: Our primary end-point are predictive. Our first primary end-point will have been met if baseline measures of personality, as measured by the NEO-Five Factor Inventory (NEO-FFI), will predict overall cognitive improvement following rehabilitation. Likewise, our second primary end-point will have been met if baseline measures of brain connectivity predict specific improvements in cognitive sub-domains, following rehabilitation. Cognitive improvement will be measured according to changes from visit 1 to visit 2 for the following neuropsychological tests: Symbol Digit Modalities Test (SDMT), California Verbal Learning Test 2nd Edition (CVLT), Brief Visuospatial Learning Test Revised (BVMT-R), MS Neuropsychological Screening Questionnaire (MSNQ), Delis-Kaplan Executive Function System (DKEFS) Sorting Test, Tower of London (TOL), Elithorn's Perceptual Maze Test (EPMT).

	Day 0 (Visit 1)	Day 90 (Visit 2)
NEO Five Factor Inventory (NEO-FFI)	X	X
Symbol Digit Modalities Test (SDMT)	X	X
California Verbal Learning Test Second Edition (CVLT)	X	X
Brief Visuospatial Memory Test Revised (BVMT)	X	X
MS Neuropsychological Screening Questionnaire (MSNQ)	X	X
Delis Kaplan Executive Function System Tower Test (DKEFS-TT)	X	X
Delis Kaplan Executive Function System Sorting Test (DKEFS-ST)	X	X
Elithorn's Perceptual Maze Test (EPMT)	X	X
Multiple Sclerosis Quality of Life (MSQoL)	X	X
Beck Depression Inventory Fast Screen (BDI-FS)	X	X
Fatigue Severity Scale (FSS)	X	X

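### Aim 2 plans no clinical reference model, so nothing written stops a connectome that only mirrors baseline score, age or disability from being credited with predicting improvement

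*SAP*

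**What the plan says.** Protocol 2.1 sets the success criterion: "our second primary end-point will have been met if baseline measures of brain connectivity predict specific improvements in cognitive sub-domains". Improvement there is the change from visit 1 to visit 2 on the listed tests. The SAP, under aim 1a, likewise defines it through "differences in cognitive scores between baseline assessment during visit 1 and post-rehabilitation assessment at visit 2".

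For aim 2 the SAP (repeated in Protocol 17.1) says "we intend to employ linear machine/statistical learning techniques, such as partial least squares regression". On model choice it says "Models will be selected according to the distribution and dimensionality of our connectome variables", with the decision left until analysis. On assessment it says "fit of the models will be assessed using k-fold cross validation". It gives no number of folds, fit metric, threshold or comparator.

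The nearest text to an adjustment is in Protocol 3.1: "we will use a multi-parametric approach in which we account for cerebral pathology, such as regional gray matter atrophy". The rest of that list is white matter damage, lesions, tract integrity and connectivity, so every item is an imaging measure.

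Hypothesis 2a in Protocol 1.2 goes further than prediction. It expects that "individual differences in structural and functional connectome disturbances will in part explain differences in participant responses to cognitive rehabilitation".

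The data for a reference model are already part of the plan. Protocol 10.4 says "We will be collecting MRI and EDSS information for subjects from the database" of the parent study, Protocol 10.2 lists demographic and cognitive test data, and education is an eligibility criterion in 6.1.

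**The concern.** Cross-validation shows whether a model predicts new participants better than their mean. It does not show whether the connectome carries anything that a birth date, a disability score or the baseline test would not. Connectome damage plausibly goes with age, disability and baseline cognition, and the sample is wide on these: above age 18 with no upper limit, and EDSS up to 6.5 (Protocol 6.1). If those variables also relate to change, a connectome with no link of its own to change can still show positive cross-validated fit.

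At stake is the meaning of a primary end-point. The study could report that connectivity identifies who benefits from training when a short baseline test would have done as well. That would not support hypothesis 2a. It would also weaken the suggestion in Protocol 3.1 that baseline cerebral pathology could be used to predict response.

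**Working it through.** **The plan's own figure.** The only sample-size figure is 41 participants for an effect size of 0.38 at 80% power (Protocol 17.2). It concerns Conscientiousness (aim 1). Read as a correlation tested one-sided at 0.05, it is nearly reproduced: ((1.645 + 0.842) / atanh(0.38))² + 3 = 41.6, or 42. It says nothing about aim 2, for which no precision or power figure is given. Planned enrolment is 50 (Protocol 5.1).

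**Step 1: baseline and raw change.** Assume equal variances at the two visits and test-retest correlation ρ, which the documents do not state. Then corr(baseline, change) = -√((1 - ρ)/2).

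| ρ (assumed) | corr(baseline, change) | R2 |
|---|---|---|
| 0.6 | -√0.20 = -0.45 | 0.20 |
| 0.7 | -√0.15 = -0.39 | 0.15 |
| 0.8 | -√0.10 = -0.32 | 0.10 |
| 0.9 | -√0.05 = -0.22 | 0.05 |

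This relation is mechanical and needs no treatment effect.

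**Step 2: what a mirror inherits.** If a connectome score correlates c with baseline and has no other link to change, its correlation with change has size c × |corr(baseline, change)|. With c assumed to be 0.4 to 0.6, this runs from 0.4 × 0.22 = 0.09 to 0.6 × 0.45 = 0.27.

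**Step 3: the planned type of method.** A simulation used one-component partial least squares, 5-fold cross-validation, 200 connectome features and N = 41 or 50, with 400 runs per setting. One clinical score explains 10%, 20% or 30% of the variance of change. In the mirroring settings, 30% of features correlate 0.4 or 0.6 with that score. No feature has its own link to change. All these values are assumptions. By Step 1, baseline alone would supply the 10% and 20% cases at ρ = 0.8 and 0.6; the 30% case would need other variables as well.

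| Clinical R2 | Mirroring connectome: runs with cross-validated R2 above 0 |
|---|---|
| 0.10 | 51% to 58% |
| 0.20 | 76% to 83% |
| 0.30 | 92% to 97% |

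A connectome unrelated to the clinical score had R2 above 0 in 16% to 26% of runs. When the mirroring connectome was added to the clinical score in the same folds, the median change in cross-validated R2 was -0.08 to -0.11, and it was positive in 17% to 26% of runs. The comparison therefore separates a mirror from added information; connectome-only fit does not.

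R2 above 0 is a convenience for the illustration. The plan states no such rule.

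**The case against.** **It is a prediction aim.** A marker that works through age or disability still predicts, and the end-point asks for no more. The documents nowhere claim that MRI beats or adds to clinical variables. This stands, and it is why the end-point should not be rewritten as a test of increment. It does not settle hypothesis 2a, which speaks of explaining differences in response.

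**Protocol 3.1 already accounts for pathology.** It does, and this deserves acknowledgement, but only for imaging measures.

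**Predictors are not restricted.** A reader might infer that the aim 2 model will hold connectome variables only. The SAP does not say so: it ties model choice to those variables but lists no predictors. What can be said is that no clinical variable or comparator is named.

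**A proxy would count as success.** A reader might infer this too. With no metric or threshold for prediction, the documents support only the weaker statement that nothing written excludes it. Nor are the simulated percentages error rates of the planned analysis.

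**Adjustment may remove the effect.** EDSS and baseline score may be consequences of connectome damage, so demanding a gain beyond them could hide a real pathway. Power is also low. In an easy case (one known connectome score, four clinical predictors, n = 50, 5-fold, permutation at 0.05, 400 runs), a true partial correlation of 0.3 was detected in about 45% of runs and 0.38 in about 62%. Details of the set-up shift these by several points, and many features would probably do worse. This stands against using the increment as the only gate, but not against reporting it.

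**Conclusion.** The concern holds in a limited form. Aim 2 has no clinical comparator, and nothing in the written criterion prevents a connectome that only mirrors age, education, disability or baseline cognition from being credited. The baseline score is the strongest case, since its link to raw change follows from how change is calculated: about -0.45 to -0.22 under equal variances and retest correlations of 0.6 to 0.9.

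The direction is secure and the size is not, because every correlation used is assumed. The gap limits what may be concluded under hypothesis 2a. It does not make the predictive end-point invalid, and it does not show that a false success is likely. It should be corrected in the SAP before analysis, particularly as model choice is left open until then.

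**What to change.** In the SAP, for each cognitive sub-domain, fit in the same folds:

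- (a) a reference model with age, education and the baseline score of that sub-domain, adding EDSS as a sensitivity analysis;
- (b) the connectome-only model;
- (c) the reference model plus connectome features.

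Report cross-validated R2 for all three, and the increment of (c) over (a) with a permutation test. State in advance that the connectome will be said to explain response, or to add to its prediction, only where the increment supports this. Otherwise describe the result as prediction not shown to go beyond clinical variables. Do not make the increment the sole rule for meeting the second primary end-point, and say why: EDSS and baseline score may lie on the pathway from connectome damage to response.

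The cost is two further model fits per sub-domain, plus the EDSS sensitivity fits, with no new visits or data. The headline figure for the connectome will probably be smaller. With 41 to 50 participants the increment will be imprecise, so an unsupportive increment should not be read as proof that the connectome adds nothing.
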